- d. **COVID-19 screening:** COVID-19 screening will be done at screening and Day -1. A subsequent COVID-19 test can be performed if participants admitted for residence develop COVID-19 like symptom(s).
- e. **Vital signs (supine BP, pulse rate):** Vital signs will be collected before dosing.
- f. **COVID-19 questionnaire:** Check exposure to positive participant, residence or travel in area of high incidence and COVID-19 related signs and symptoms.
- g. **COVID-19 testing:** The testing for COVID-19 pathogen by PCR will be performed screening and D-1. A subsequent COVID-19 test can be performed if participants admitted for residence develop COVID-19 like symptom(s).
- h. **COVID-19 check temperature:** To be done twice daily during residence.
- i. **OC dosing:** Participants will be dosed with OC following an overnight fast of at least 10 hours. On the day of co-administration of OC and PF-06650833, the two will be administered simultaneously within 5 minutes.
- j. **PF-06650833 QD dosing:** The daily dose of PF-06650833 will be administered at approximately 08:00 ±2 hours.
- k. **OC PK blood sample:** PK blood samples are to be collected at predose, at 30 minutes and 1, 1.5, 2, 4, 6, 8, 12, 24, 36 and 48 hours post OC dose in Periods 1 and 2.
- l. **OC PK blood sample:** The 24 hour OC PK samples on Period 2 Day 11 must be collected pre PF-06650833 dose.
- m. **Period 2:** There is no washout phase between Period 1 and Period 2.
- n. **Follow-up:** Participants will have a telephone contact at least 28 calendar days, and up to 35 calendar days after the last administration of the investigational product(s). At the discretion of the investigator, telephone contact may be substituted with an on-site visit in case of additional follow-up of open AEs or clinically significant laboratory findings

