2.2. Study Design

This is a Phase 1, fixed-sequence, multiple-dose, open-label study of the effect of multiple dose PF-06650833 on single dose OC PK in healthy female participants. A total of approximately 10 healthy female participants will be enrolled in the study. The study will consist of 2 periods in a single fixed sequence. Participants will be screened within 28 days of the first dose of investigational product in Period 1. Participants will report to the CRU the day prior to Day 1 dosing in Period 1. Participants will remain in the CRU for a total of 16 days and 15 nights. There will be no washout period.

[figure not shown]
On Period 1 Day 1, participants will be dosed with a single administration of OC in the form of 1 PORTIA® (EE and LN) or equivalent tablet, orally. OC (EE and LN) PK will then be assessed at pre-dose and over 48 hours, post OC dosing. Period 1 will be immediately followed by Period 2 with no washout, in which participants will be dosed orally with PF-06650833 400 mg MR QD for 9 days followed by administration of a single dose of OC on the morning of Day 10. OC PK will be assessed at pre-dose and for 48 hours following OC dosing. On Day 10, the morning dose of PF-06650833 and the single OC dose will be administered simultaneously within 5 minutes. Dosing with PF-06650833 400 mg PO QD will continue until Day 11 (Table 2). Participants will be discharged on Day 12 only after review of safety laboratory by the PI. [Figure 1](#) shows the schematic of Study Design.

Table 2. Study Design and Treatments

Period 1	Washout	Period 2
Treatment R	None	Treatment T

Treatment R: Single dose of OC in the form of 1 PORTIA® (EE and LN) or equivalent oral tablet, containing EE 30 µg and LN 150 µg.

Treatment T: Single dose of combination OC in the form of 1 PORTIA® (EE and LN) or equivalent oral tablet, containing of EE 30 µg and LN 150 µg on the morning of Day 10 following 9 days of PF-06650833 dosed at 400 mg PO QD. Dosing with PF-06650833 at 400 mg PO QD will continue through until Day 11.

Figure 1. Schematic of Study Design

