3.5.1. Adverse Events

An adverse event will be considered a Treatment-Emergent Adverse Event (TEAE) if the event started during the effective duration of treatment. All events that start on or after the first dosing day and time/start time, if collected, but before the last dose plus the lag time (28 days) will be flagged as TEAEs. The algorithm will not consider any events that started prior to the first dose date. Any events occurring following start of treatment or increasing in severity and occur in either of the following three phases: OC, PF-06650833 (Days 1-10 of

Period 2), OC+PF-06650833 (Days 10-12 of Period 2), will be counted as treatment emergent. Events that occur in a non-treatment period (for example, Follow-up) will be counted as treatment emergent and attributed to the previous treatment taken.

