6.2. Safety Summaries and Analyses

All safety analyses will be performed on the safety population and summarized in accordance with Pfizer Data Standards.

All clinical AEs, SAEs, TEAEs, withdrawal due to AEs, ECGs, vital signs and safety laboratory data will be reviewed and summarized on an ongoing basis during the study to evaluate the safety of participants.

Safety data will be summarized descriptively through appropriate data tabulations, descriptive statistics, categorical summaries, and graphical presentations, where appropriate. Categorical outcomes (eg, AEs) will be summarized by participant counts and percentage. Continuous outcome (eg, blood pressure, pulse rate, etc.) will be summarized using N, mean, median, standard deviation, etc. Change from baseline (CFB) in laboratory data, and vital signs will also be summarized. Participant listings will be produced for the safety endpoints accordingly.

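### SAP 3.5.1 gives the OC+PF-06650833 adverse-event group about 29 days of observation against 3 for OC alone and 9 for PF-06650833 alone, and no time at risk is shown beside the percentages

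*SAP*

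**What the plan says.** SAP 3.5.1 sorts adverse events into three phases: OC alone, PF-06650833 alone (Period 2 Days 1 to 10), and the combination, "OC+PF-06650833 (Days 10-12 of Period 2), will be counted as treatment emergent". Events that start after first dosing and "before the last dose plus the lag time (28 days) will be flagged as TEAEs". For time outside the phases the rule is: "Events that occur in a non-treatment period (for example, Follow-up) will be counted as treatment emergent and attributed to the previous treatment taken".

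The design in SAP 2.2 fixes the calendar. "Period 1 will be immediately followed by Period 2 with no washout". The second OC tablet is given "on the morning of Day 10 following 9 days of PF-06650833 dosed at 400 mg PO QD", and "Dosing with PF-06650833 at 400 mg PO QD will continue through until Day 11". Discharge is on Day 12. Footnote n to the Schedule of Activities (Protocol 1.3) sets follow-up: "Participants will have a telephone contact at least 28 calendar days, and up to 35 calendar days after the last administration".

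On presentation, SAP 6.2 says "Categorical outcomes (eg, AEs) will be summarized by participant counts and percentage". SAP 6.2.1 refers to sponsor reporting standards, which are not part of the documents. Table 5 in SAP 5.2 has only two safety-reporting groups: R for Period 1 and T for Period 2.

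**The concern.** The share of participants with at least one event rises with the time they are watched. The follow-up rule adds about four weeks to one phase only. With no washout, neither other phase has follow-up time of its own for a participant who reaches the Day 10 OC dose.

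The secondary objective is the safety of PF-06650833 when given together with OC, and the combination column is its direct readout. With about 10 participants planned, each participant with an event moves a column by about 10 percentage points (1/10). One or two unrelated events in the weeks after discharge would therefore be visible in the combination column. A reader comparing it with OC alone would have no denominator with which to discount them.

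Three details of the rules are also unsettled:

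- Day 10 belongs to two phases.
- Section 3.5.1 and Table 5 imply different columns.
- The lag sentence and the follow-up sentence classify late events differently.

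**Working it through.** **Day count.** The plan's own figure is a stay of 16 days with 15 nights. Day -1 (1) + Period 1 Days 1 to 3 (3) + Period 2 Days 1 to 12 (12) = 16 days and 15 nights. This matches only if Period 1 Day 3 and Period 2 Day 1 are separate days; if they were the same day the count would be 15 days and 14 nights.

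**Windows, dose to dose, for a participant dosed on Period 2 Days 10 and 11.**

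| Group | From | To | Days |
|---|---|---|---|
| OC | Period 1 Day 1 | Period 2 Day 1 | 3 |
| PF-06650833 | Period 2 Day 1 | Period 2 Day 10 | 9 |
| OC+PF-06650833 | Period 2 Day 10 | Day 11 + 28 days | 1 + 28 = 29 |
| of which before discharge | Day 10 | Day 12 | 2 |
| of which after discharge | Day 12 | Day 11 + 28 days | 29 - 2 = 27 (27/29 = 93%) |

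The ratios are 29/3 = 9.7 and 29/9 = 3.2. If the follow-up sentence is read without the 28-day limit, the combination window can reach 1 + 35 = 36 days.

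**Table 5 grouping.** R covers 3 days and T covers 9 + 29 = 38 days, a ratio of 38/3 = 12.7.

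**Illustration only.** The documents give no adverse-event rate. Assume a constant rate r per participant-day, no drug effect and equal detection throughout, so that P(at least one event) = 1 - exp(-r × days).

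| Assumed r | OC, 3 d | PF-06650833, 9 d | OC+PF-06650833, 29 d | OC+PF-06650833 to discharge, 2 d |
|---|---|---|---|---|
| 0.005 | 1.5% | 4.4% | 13.5% | 1.0% |
| 0.01 | 3.0% | 8.6% | 25.2% | 2.0% |
| 0.02 | 5.8% | 16.5% | 44.0% | 3.9% |

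**How far this depends on equal detection.** Suppose follow-up captures events at a fraction f of the in-clinic rate. The combination window then counts as 2 + 27f in-clinic days. It equals the 3 days of OC alone when f = 1/27 = 0.04, and the 9 days of PF-06650833 alone when f = 7/27 = 0.26. Under a constant rate, the excess over OC alone survives very poor capture in follow-up. The excess over PF-06650833 alone needs follow-up to capture about a quarter of the in-clinic rate.

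**Late events.** For an event starting 28 to 35 days after the last dose, the lag sentence says it is not treatment emergent. The follow-up sentence says it is, and assigns it to the last treatment. The Schedule of Activities has adverse-event monitoring at the follow-up contact, so such events can be collected.

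**The case against.** The strongest reply has five parts.

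- **The layout is not settled.** Section 3.5.1 uses the three phases to define treatment emergence and does not prescribe table columns. Table 5 has two groups. This stands as a reason to cite both, but the two-group reading makes the imbalance larger (38 days against 3).
- **The sponsor's standards may print days at risk or a follow-up split.** This is possible and cannot be checked. The missing denominator is established only for the visible text, and the attribution sentence is explicit either way.
- **Detection is not constant.** Events are monitored continuously during confinement, then at one telephone contact, with no scheduled laboratory tests, ECGs or vital signs after discharge. This stands. A reader might infer from the illustration that the combination column will show about 25% against 3%; the documents do not support that or any other particular figure.
- **No dosing is not the same as no exposure.** Day 12 is only about a day after the last PF-06650833 dose and two days after the OC tablet. A reader might call the 27 post-discharge days off-drug, but the documents do not show that. Moving all late events out of the combination group could hide a delayed effect, so the remedy has to keep a combined subtotal.
- **The consequence is limited.** SAP 5.1 sets no hypotheses or decision rules for safety, participant listings will be produced, and the PK result is untouched. This also stands. It limits the weight of the point but does not remove the imbalance.

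**Conclusion.** The point holds as a matter of presentation and clarity. For participants dosed on Period 2 Days 10 and 11, the stated rules give windows of 3, 9 and 29 days, or 3 and 38 under Table 5, and about 27 of the 29 days fall after discharge. With percentages and no visible time at risk, the combination column can look worse than OC alone through window length alone.

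The window lengths follow from the documents. The effect on incidence does not: it rests on an assumed rate and on how completely one telephone contact captures events. For a participant who stops before Day 10, follow-up events go to OC or PF-06650833 alone, so the 29 days do not apply.

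A reader might go further and infer a false safety finding or an inflated error rate. Nothing in the plan supports that, because the safety comparison is descriptive and untested. The harm is a potentially misleading table.

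**What to change.** Change SAP 3.5.1, 5.2 (Table 5) and 6.2.1 as follows:

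1. Keep follow-up events as treatment emergent and in the overall total.
2. Within the OC+PF-06650833 group, show onset up to Day 12 discharge and onset after discharge as separate sub-columns, with a combined subtotal so that no delayed event is lost from the group.
3. Print participant-days at risk under every column.
4. Reconcile the three phases of 3.5.1 with the two groups of Table 5, and state how Day 10 onsets are assigned, for example by onset before or after the OC dose where a time is recorded.
5. Apply one treatment-emergent cut-off to events starting 28 to 35 days after the last dose.

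The cost is one more table split, a line of participant-days and some SAP wording. Dosing, visits, data collection and safety reporting do not change.

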3.5.2. Laboratory Data

Safety laboratory tests will be performed as described in the protocol.

To determine if there are any clinically significant laboratory abnormalities, the haematological, clinical chemistry (serum) and urinalysis safety tests will be assessed against the criteria specified in the sponsor reporting standards. The assessment will take into account whether each participant's baseline test result is within or outside the laboratory reference range for the particular laboratory parameter.

Plot of laboratory parameter(s) value and plot of change from baseline may be requested for parameters changing significantly from baseline.

3.5.3. Vital Signs Data

Supine measurements will be taken at times detailed in the Schedule of Activities given in the protocol.

The following vital signs endpoints will be determined:

- The minimum and maximum systolic and diastolic blood pressures and the minimum and maximum pulse rates over all measurements taken post-dose.
- The maximum increase and maximum decrease from baseline over all measurements taken post-dose for systolic and diastolic blood pressures and pulse rates.

The maximum increase from baseline will be calculated by firstly subtracting the baseline value from each post-dose measurement to give the change from baseline. The maximum of these values will then be selected, except in the case where a participant does not show an increase. In such an instance, the minimum decrease should be taken.

Similarly, the maximum decrease from baseline will be determined by selecting the minimum value of the changes from baseline. In cases where a participant does not show a decrease, the minimum increase should be taken.

Plot of vital signs parameter(s) values and plot of change from baseline may be requested for parameters changing significantly from baseline.

3.5.4. ECG Results

PR, QT, RR and QTc intervals, QRS and heart rate will be recorded at each assessment time indicated in the Schedule of Activities given in the protocol. QTcF will also be presented and will be derived using Fridericia's heart rate correction formula.

If not supplied, QTcF will be derived using Fridericia's heart rate correction formula:

$$\text{QTcF} = \text{QT} / (\text{RR})^{1/3} \quad \text{where RR} = 60/\text{HR} \text{ (if not provided)}$$

The maximum absolute value (post-dose) and the maximum increase from baseline for QTcF, PR, RR and QRS, over all measurements taken post-dose, will be determined.

The maximum increase from baseline will be calculated by first subtracting the baseline value from each post-dose measurement to give the change from baseline. The maximum of these values will then be selected, except in the case where a participant does not show an increase. In such an instance, the minimum decrease should be taken.

CCI

4. ANALYSIS SETS (POPULATIONS FOR ANALYSIS)

Data for all participants will be assessed to determine if participants meet the criteria for inclusion in each analysis population prior to unblinding and releasing the database and classifications will be documented per standard operating procedures.

Table 3. Analysis Populations

Population	Description
Enrolled	All participants who sign the informed consent document (ICD). A participant will be considered enrolled if the informed consent is not withdrawn prior to participating in any study activity after screening.
Assigned to investigational product	All participants who sign the ICD and meet all eligibility criteria.
PK Concentration Analysis Set	All participants who receive at least 1 dose of investigational product and have at least 1 plasma concentration value reported in at least 1 period.
PK Parameter Analysis Set	All participants who receive at least 1 dose of investigational product and have at least 1 of the PK parameters of primary interest reported in at least 1 period.

Population	Description
Evaluable	All participants enrolled to investigational product and who take at least 1 dose of investigational product.
Safety	All participants enrolled to investigational product and who take at least 1 dose of investigational product. Participants will be analyzed according to the product they actually received.

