6. STUDY INTERVENTION(S) AND CONCOMITANT THERAPY

Study intervention is defined as any investigational intervention(s), marketed product(s), placebo, or medical device(s) intended to be administered to a study participant according to the study protocol.

For the purposes of this protocol, the term investigational product may be used synonymously with study intervention.

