6.1. Study Intervention(s) Administered

For the purposes of this protocol, study intervention refers to PF-06650833.

PORTIA® (or equivalent) is an NIMP.

PF-06650833 200-mg MR tablets will be provided by Pfizer to the CRU in bulk along with individual dosing containers and desiccants for unit dosing.

Study intervention will be presented to the participants in individual dosing containers.

PORTIA® (or equivalent) will be supplied by the CRU. All PORTIA® or equivalent oral tablet used in this study should be from the same manufacturing batch.

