6.1.1. Administration

Following an overnight fast of at least 10 hours, participants will receive one PORTIA® or equivalent tablet on Period 1 Day 1 at approximately 08:00 hours (plus or minus 2 hours). On the days of co-administration of OC and PF-06650833 (Period 2 Day 10), one PORTIA® or equivalent tablet should be administered simultaneously within 5 minutes of two 200-mg PF-06650833 MR tablets dosing. Investigator site personnel will administer investigational product during each period with ambient temperature water to a total volume of approximately 240 mL. Additional water is allowed if needed to complete administration of the entire dose. Participants will swallow the investigational product whole, and will not manipulate or chew the investigational product prior to swallowing.

In order to standardize the conditions on PK sampling days, all participants will be required to refrain from lying down (except when required for BP, pulse rate, and ECG measurements), eating, and drinking beverages other than water 4 hours after dosing.

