FSH	follicle-stimulating hormone
GCP	Good Clinical Practice
GGT	gamma-glutamyl transferase
GI	gastrointestinal
GLP	Good Laboratory Practice
HBcAb	hepatitis B core antibody
HBsAb	hepatitis B surface antibody
HBsAg	hepatitis B surface antigen
HCV	hepatitis C virus

Abbreviation	Term
HCVAb	hepatitis C antibody
HIV	human immunodeficiency virus
HR	heart rate
HRT	hormone replacement therapy
HS	hidradenitis suppurativa
HSV	herpes simplex virus
IB	investigator's brochure
IC ₅₀	the concentration of an inhibitor where the response (or binding) is reduced by half
ICD	informed consent document
ICH	International Council for Harmonisation of Technical Requirements for Pharmaceuticals for Human Use
ID	identification
IGRA	Interferon Gamma Release Assay
IND	investigational new drug
INR	international normalized ratio
IP	investigational product
IPAL	Investigational Product Accountability Log
IQMP	integrated quality management plan
IR	immediate release
IRAK4	IL -1 receptor associated kinase 4
IRB	institutional review board
IV	intravenous
k _{el}	terminal phase rate constant
K ₂ EDTA	dipotassium ethylenediaminetetraacetic acid
LBBB	left bundle branch block
LFT	liver function test
LN	levonorgestrel
MAD	multiple ascending dose
MATE	multidrug and toxin extrusion protein
MCH	mean corpuscular hemoglobin
MCHC	mean corpuscular hemoglobin concentration
MCV	mean corpuscular volume
MR	modified release
mRNA	messenger ribonucleic acid
msec	millisecond
N/A	not applicable
NIMP	Non Investigational Medicinal Product
NOAEL	no-observed-adverse-effect level
OAT	organic anion transporter
OATP	organic anion-transporting polypeptide
OC	oral contraceptive

Abbreviation	Term
OCT	organic cation transporter
PCR	polymerase chain reaction
PCRU	Pfizer Clinical Research Unit
PD	pharmacodynamic(s)
P-gp	P-glycoprotein
PI	principal investigator
PK	pharmacokinetic(s)
PO	by mouth
PPD	purified protein derivative
PT	prothrombin time
PTR	peak-to-trough ratio
PVC	premature ventricular contraction/complex
QD	once daily
QFT-G	QuantiFERON-TB Gold IN-Tube
QID	4 times a day
QTc	corrected QT
QTcF	corrected QT (Fridericia method)
qual	qualitative
RA	rheumatoid arthritis
RBC	red blood cell
RNA	ribonucleic acid
SAD	single ascending dose
SAE	serious adverse event
SAP	statistical analysis plan
SARS-CoV-2	severe acute respiratory syndrome coronavirus 2
SCr	serum creatinine
SD	standard deviation
SoA	schedule of activities
SOC	system organ class
SOP	standard operating procedure
SRSD	single reference safety document

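### Does a participant who takes only the Period 1 oral contraceptive drop out of the Safety and PK sets?

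*SAP*

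**What the plan says.** SAP Section 4 (Table 3) defines the Safety and Evaluable sets as "All participants enrolled to investigational product and who take at least 1 dose of investigational product". The PK Concentration and PK Parameter sets use the same dosing condition and add that a concentration, or a primary PK parameter, must be available from one period or more. Protocol 9.2 and 9.3.1 carry the same rules.

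The term is not used uniformly:

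- Protocol 6.1 says "For the purposes of this protocol, study intervention refers to PF-06650833" and "PORTIA® (or equivalent) is an NIMP". Protocol Appendix 8 spells out the abbreviation as "Non Investigational Medicinal Product".
- Protocol 6 says "the term investigational product may be used synonymously with study intervention". The general definition of study intervention in the same section also covers marketed products.
- Protocol 6.1.1 says "Investigator site personnel will administer investigational product during each period", although Period 1 contains only the OC.
- SAP 2.2, like Protocol 1.1 and 4.1, says "Participants will be screened within 28 days of the first dose of investigational product in Period 1".

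The Safety row of SAP Table 3 adds "Participants will be analyzed according to the product they actually received".

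**The concern.** If the restriction in Protocol 6.1 is joined to the synonym sentence in Protocol 6, the OC is not investigational product. A woman who takes the OC on Period 1 Day 1 and leaves before Period 2 Day 1 has then taken none, and she meets no analysis-set definition except Enrolled and Assigned. SAP 6.2 runs all safety analyses on the Safety population, so her adverse events would be on the CRF but absent from the Treatment R tables. Her reference profile would also be missing from the PK summaries. The awkward case is a participant who leaves because of an event after the OC, since she is the one the OC-phase table most needs to show.

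The same loose usage appears in the eligibility, dietary and concomitant-treatment windows of Protocol 5.2, 5.3.1 and 6.8. Some of these count back from the first study intervention and others from the first investigational product.

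**Working it through.** **1. Which reading the SAP supports**

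| Place | What it implies for an OC-only participant |
|---|---|
| Protocol 6.1 | Excluded, if investigational product means study intervention and nothing else |
| Protocol 6 | Included: the general definition covers marketed products, and the synonym is permissive |
| Protocol 1.1, 4.1, 6.1.1; SAP 2.2 | Included: the OC dose in Period 1 is counted as investigational product |
| SAP 3.5.1 | Included: OC alone is one of three phases for treatment-emergent events |
| SAP 5.2, Table 5 | Included: Treatment R has Period 1 as its safety reporting period |
| SAP Section 4, PK sets | Consistent with inclusion: one period of data is enough |

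The SAP itself contains neither the Protocol 6.1 restriction nor the non-investigational label. Excluding her means importing a definition that contradicts SAP 2.2.

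**2. Length of the gap**

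- Calendar: Day -1 (1) + Period 1 Days 1-3 (3) + Period 2 Days 1-12 (12) = 16 days, with 15 nights. This reproduces the stated confinement, so Period 2 Day 1 falls 3 days after the OC dose.
- The gap is nominally 72 h. The ±2 h dosing windows give 68 to 76 h.

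**3. Chance that anyone leaves in the gap**

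Protocol 9.5 enrols about 10 to have 8 or more complete: 8/(1 − 0.20) = 10, where 20% is implied and not stated. Dropout timing is not given. Assume two non-completers leaving uniformly over time.

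- *Losses in confinement only.* Period 2 Day 12 is 14 days after the OC dose, so the gap share is 3/14 = 0.214. At least one in the gap: 1 − (11/14)² = 0.383. Both: (3/14)² = 0.046.
- *Losses through follow-up.* Protocol 4.4 counts completion to the last visit, and follow-up is 28-35 days after the last dose. That dose (Period 2 Day 11) is day 13 after the OC dose, so the end is day 13 + 28 = 41 to 13 + 35 = 48. The gap share is 3/48 to 3/41 = 0.063 to 0.073. At least one: 1 − (45/48)² = 0.121 to 1 − (38/41)² = 0.141. Both: about 0.004 to 0.005.
- With one non-completer, the chance through follow-up is 6.3% to 7.3%. With none it is zero.

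**4. Effect if the excluding reading were applied**

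- Treatment R denominator: 9 with one leaver, 8 with two, instead of 10.
- One event in another participant: 1/10 = 10.0% becomes 1/9 = 11.1% or 1/8 = 12.5%.
- One event in a sole leaver: 1/10 = 10.0% becomes 0/9 = 0%.

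**5. Effect on the primary ratio**

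SAP 5.2 and 6.1.1 do not tie the mixed model to a named set. Suppose it uses the PK Parameter set. With a random participant effect, known variance components and within-participant correlation ρ, adding reference-only participants to the complete pairs multiplies the standard error of the log ratio by:

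- 9 pairs + 1: √(0.95 + 0.05ρ) = 0.982 at ρ = 0.3 and 0.9975 at ρ = 0.9.
- 8 pairs + 2: √(0.90 + 0.10ρ) = 0.964 at ρ = 0.3 and 0.995 at ρ = 0.9.

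Inclusion therefore shortens the standard error by 0.25% to 3.6%. The released documents give no variability figure, so ρ is an assumption.

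**The case for a change.** The best argument for a written rule is that the protocol's only explicit classification of the OC is the non-investigational label, and that label points to exclusion. The sentence about the product actually received assigns a treatment to people already in the Safety set; it does not say which product admits them. SAP Section 4 also requires membership to be decided and documented before database release, which favours a stated rule over an inferred one. Departure is not random either: an adverse event after the OC is a plausible reason to leave in those three days, so a uniform model may understate the case that matters.

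The inconsistency stands, and so does the point about the received-product sentence. They do not outweigh the rest of the SAP. The OC phase and the Treatment R safety period have their own places in the reporting, and the design section counts the OC dose as investigational product. The classification step before release is also where a data manager or statistician would meet an OC-only participant and place her by that text. Her events are collected from consent under Protocol 8.3.1 whichever reading is used.

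The time windows are a separate matter of wording. Protocol 4.1 and Protocol 8 state the same 28-day screening window, one by investigational product in Period 1 and the other by study intervention, so the protocol treats these as the same dose. Eligibility is checked at Screening and Day -1, both before the OC. The passages should use one term, but the analysis does not depend on it.

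**Conclusion.** The wording is inconsistent between Protocol 6.1 and the design, administration and reporting sections, but this is a gap that analysts fill sensibly. The SAP's own text leads to including a participant who takes only the OC in the Safety and PK sets, so a clarifying line would record the expected classification and alter no result.

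Nothing at all turns on it unless someone leaves within about 72 h of the OC dose. That chance is about 12-14% with two non-completers spread uniformly through follow-up and 38% if both losses fall in confinement. It is lower with fewer losses and could be higher if early departures cluster after the OC. Were the excluding reading nevertheless applied, the damage would be confined to the Treatment R safety tables (denominator 8 or 9 instead of 10, and possibly one missing event) and the descriptive PK summaries. The primary ratio would be essentially untouched: its standard error differs by at most 3.6% for assumed correlations of 0.3 to 0.9. No change to the plan is needed.
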